# 8. Satisfy 1 of the following:

- a. Females: Non-pregnant and non-lactating; surgically sterile (e.g., tubal occlusion, hysterectomy, bilateral salpingectomy, bilateral oophorectomy), post-menopausal (defined as 12 months of spontaneous amenorrhea in females > 55 years of age or, in females ≤ 55 years, 12 months of spontaneous amenorrhea without an alternative medical cause and follicle-stimulating hormone (FSH) levels in the postmenopausal range for the laboratory involved), abstinent\*, or if engaged in sexual relations of child-bearing potential, patient is using an acceptable contraceptive method (refer to Section 6.3.1) from time of signing the informed consent form until at least 13 weeks after the last dose of Study Drug administration.
- b. Males: Surgically sterile, abstinent, or if engaged in sexual relations with a female of child-bearing potential, patient is utilizing an acceptable contraceptive method (refer to Section 6.3.1) from the time of signing the informed consent form until at least 13 weeks after the last dose of Study Drug administration.

\*Abstinence is only acceptable as true abstinence, i.e., when this is in line with the preferred and usual lifestyle of the patient. Periodic abstinence (e.g., calendar, ovulation, symptothermal, post-ovulation methods), declaration of abstinence for the duration of a trial and withdrawal are not acceptable methods of contraception).

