# 6.3 Restriction on the Lifestyle of Subjects

# 6.3.1 Contraception Requirements

All male subjects and women of childbearing potential must refrain from sperm/egg donation and either be abstinent† or practice effective contraception from the time of signing the informed consent form until at least a period of 13 weeks after their last dose of study treatment.

Male subjects engaged in sexual relations with a female of child-bearing potential must also encourage their female partner to use effective contraception from the time of signing the informed consent until a period of 13 weeks after the subject's last dose of study treatment.

For the purposes of this study, women of childbearing potential are defined as any female who has experienced menarche, and who does not meet one of the following conditions:

- Postmenopausal: 12 months of spontaneous amenorrhea in females > 55 years of age or, in females ≤ 55 years, 12 months of spontaneous amenorrhea without an alternative medical cause and FSH levels in the postmenopausal range for the laboratory involved
- 6 weeks after surgical bilateral oophorectomy with or without hysterectomy
- Post hysterectomy

For the purposes of the study, effective contraception is defined as follows:

For male subjects:

- Effective male contraception includes a vasectomy with negative semen analysis at follow-up, or the use of condoms together with spermicidal foam/gel/film/ cream/suppository
- Male subjects with partners that are pregnant must use condoms as contraception to ensure that the fetus is not exposed to the Study Drug

For female subjects and female partners of male subjects:

- Using 2 of the following acceptable methods of contraception: surgical sterilization (e.g., bilateral tubal ligation), hormonal contraception, intrauterine contraception/device, or any 2 barrier methods (a combination of male or female condom\* with diaphragm, sponge, or cervical cap) together with spermicidal foam/gel/film/cream/suppository
- **†Note:** Abstinence is only acceptable as true abstinence, i.e., when this is in line with the preferred and usual lifestyle of the patient. Periodic abstinence (e.g., calendar, ovulation, symptothermal, post-ovulation methods), declaration of abstinence for the duration of a trial and withdrawal are not acceptable methods of contraception.

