#### 9.5.4 Contraception and Pregnancy

Subjects must continue to use appropriate contraception with their partners, or refrain from sexual activity, as described in Section 6.3.1. If a subject becomes pregnant or a pregnancy is suspected, or if a male subject makes or believes that he has made someone pregnant during the Study, then the Study Center staff must be informed immediately. An Initial Pregnancy Form should be submitted to the Sponsor or designee within 24 hours of first learning of the occurrence of pregnancy. Follow-up information including delivery or termination is reported by designating as 'Follow-up' on the Pregnancy Forms and reported within 24 hours. Payment for all aspects of obstetrical care, child or related care will be the subject's responsibility. Female subjects: If a suspected pregnancy occurs while on the Study (including follow-up), a pregnancy test will be performed. The subject with a confirmed pregnancy will be immediately withdrawn from treatment with Study Drug. However, the subject will be encouraged to complete the post-treatment follow-up portion of the Study to the extent that study procedures do not interfere with the pregnancy. Regardless of continued study participation, the study physician will assist the subject in getting obstetrical care and the progress of the pregnancy will be followed until the outcome

of the pregnancy is known (i.e., delivery, elective termination, or spontaneous abortion). If the pregnancy results in the birth of a child, the Study Center and Sponsor may require access to the mother and infant's medical records for an additional 8 weeks after birth. Follow-up will be performed to the extent permitted by the applicable regulations and privacy considerations. Male subjects: The progress of the pregnancy of a male subject's partner should be followed until the outcome of the pregnancy is known (i.e., delivery, elective termination, or spontaneous abortion). If the pregnancy results in the birth of a child, the Study Center and Sponsor may request access to the mother and infant's medical records for an additional 8 weeks after birth. Follow-up will be performed to the extent permitted by the applicable regulations and privacy considerations.

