# Appendix ASchedule of Procedures Continued

	Scree	ning		Treatment Period					Follow-up Period				
	Run-in #	Qual †											
Study Week	-6 to -1	-1 to 0	1	5	9	13	17	21	25	27/ET	4*	8*	13*
Study Day	-42 to -1	-7 to -1	1	29	57	85	113	141	169	183		from the ment pe	e end of riod o
Visit and Testing Window +/- Days	0	0	0	2	2	2	3	3	3	0	3	3	3
Hematology	Х			-		EVERY 14 D	DAYS (+/- 2	days) f			X h	X h	X h
Coagulation	Х		Х							Х			
Hepatitis B, C, HIV	Х												
Thyroid Panel	Х												
Inflammatory			Х			Х				Х			Х
Liver Biomarkers			Х			Х				Х			Х
Plasma PK - ISIS 703802 I			X 	X 	X 	X 	X 	X 	X 	Х	Х	Х	Х
Anti-ISIS 703802 Antibodies			Х	Х	Х	Х		Х		Х		Х	Х
FSH (women only, if applicable) j, m	Х												
Serum Pregnancy Test m	Х		Х	Х	Х	Х	Х	Х	Х	Х	Х	Х	
Archived Serum & Plasma Samples $_{j,n}$			х		х		х			Х			х
PD Panel j	Х	Х	Х	Х	Х	Х	Х	Х	Х	Х	Х	Х	Х
Extended Lipid Panel j	Х	Х	Х	Х	Х	Х	Х	Х	Х	Х	Х	Х	Х
HbA1C j	Х		Х			Х				Х			Х
Quality of Life Assessment		Х				Х				Х			
Widespread Pain Diary		Х			TO E	BE DONE AT	OUTPATIE	ENT VISITS			Х	Х	Х
Study Drug: SC Injection			WEEK	WEEKLY SUBCUTANEOUS ADMINISTRATION OF STUDY DRUG (Week 1 through Week 26/Day 176)									
Adverse Events		TO BE COLLECTED FROM TIME OF INFORMED CONSENT TO END OF FOLLOW-UP PERIOD											
Concomitant Medication			TO BE (	COLLECTE	D FROM T	IME OF INFO	ORMED CC	NSENT TO	END OF FOLL	OW-UP PE	RIOD		

1010 / 00 002 00		
Protocol		16 February 2018
Appendix A	Schedule of Procedures Continued	

CONFIDENTIAL

Amendment 1

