- m Women who are not surgically sterile or post-menopausal.
- n Serum and plasma samples will be collected and stored for follow-up exploration of laboratory findings and/or AEs (e.g., measurement of cytokine and/or chemokine levels, measurement of additional markers of kidney function, measurement of antibodies, etc.) and will be retained until completion of the final study report.
- o Treatment period is defined as the time from the first dose through one dosing interval post last dose.
- p Genetic testing will only be performed for eligibility if there is no documented genetic testing in medical history.
- q 24-hour urine sample for creatinine clearance and protein should also be obtained in the event of an eGFR (CKD-EPI) value meeting criteria specified in Sections 8.5.2 and 8.6.2.

Time (time is in reference to Study Drug administration):

1 Pre-dose

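### Footnote m in Appendix A schedules pregnancy tests by surgical sterility, so a pre-menopausal woman with only a tubal procedure, whom Section 6.3.1 counts as of childbearing potential, misses at least 10 of the 11 tests

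*Combined protocol and SAP*

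**What the plan says.** In Appendix A of Protocol Amendment 1, the row "Serum Pregnancy Test" carries footnote m, which limits it to "Women who are not surgically sterile or post-menopausal". The footnote does not define surgical sterility. The only place in the protocol that gives examples of the term as a status is inclusion criterion 8a (Section 5.1, repeated in the synopsis): "surgically sterile (e.g., tubal occlusion, hysterectomy, bilateral salpingectomy, bilateral oophorectomy".

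Section 6.3.1 sets out who can become pregnant, stated to be for the purposes of the study: "women of childbearing potential are defined as any female who has experienced menarche, and who does not meet one of the following conditions". There are three conditions: being post-menopausal, "6 weeks after surgical bilateral oophorectomy with or without hysterectomy", and having had a hysterectomy. No tubal procedure is among them. The same section treats tubal ligation as contraception, and as insufficient alone: "Using 2 of the following acceptable methods of contraception: surgical sterilization (e.g., bilateral tubal ligation", followed by the other methods.

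Section 9.5.4 repeats the contraception rule ("Subjects must continue to use appropriate contraception with their partners, or refrain from sexual activity, as described in Section 6.3.1") and provides a test for cause: "If a suspected pregnancy occurs while on the Study (including follow-up), a pregnancy test will be performed". Appendix B lists serum βhCG under Screening Tests without restricting it by sterility.

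**The concern.** The protocol uses two different populations for closely related purposes. Section 6.3.1 takes the view that a tubal procedure does not remove childbearing potential, and so asks for a second contraceptive method. Footnote m takes the view that the same procedure is enough to drop scheduled testing.

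Two protective rules depend on a pregnancy being found. Section 8.8 makes pregnancy a reason for permanent discontinuation, and Section 9.5.4 requires immediate withdrawal from treatment. For this woman, detection would rest on suspicion alone. Suspicion may also be a weaker trigger in this disease: Section 2.1 describes polycystic ovary syndrome with oligomenorrhea in these patients, and it is one of the minor diagnostic criteria, so a missed period may be less noticeable. That last step is inference; the documents give no rate.

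**Working it through.** The plan states no figure to reproduce. The check is a comparison of definitions and a count of schedule marks.

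**Step 1: compare the definitions, for a pre-menopausal woman with one procedure only.**

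| Procedure | Surgically sterile (8a) | Of childbearing potential (6.3.1) | In the test row (footnote m) |
|---|---|---|---|
| Hysterectomy | Yes | No | No |
| Bilateral oophorectomy (6 weeks or more ago) | Yes | No | No |
| Tubal occlusion | Yes | Yes | No |
| Bilateral salpingectomy | Yes | Yes | No |

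The mismatch lies in the last two rows. Reading footnote m in the light of Section 6.3.1 does not remove it, because that section itself calls tubal ligation surgical sterilization.

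**Step 2: count the scheduled tests (Appendix A, Amendment 1).**

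- Screening: 1
- Day 1, pre-dose: 1
- Weeks 5, 9, 13, 17, 21 and 25: 6
- Week 27/ET: 1
- Follow-up Weeks 4 and 8: 2

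Total: 1 + 1 + 6 + 1 + 2 = 11. There is no mark at Qualification or follow-up Week 13.

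**Step 3: count what is left for the affected woman.**

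- If footnote m governs: 0 tests remain, so 11 − 0 = 11 do not apply.
- If the Appendix B screening entry overrides it: 1 remains, so 11 − 1 = 10 do not apply.
- From Day 1 onward, 1 + 6 + 1 + 2 = 10 tests are lost on either reading.

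**Step 4: look for other checks.** The Inclusion/Exclusion Criteria row has 3 marks, all before the first dose (Screening, Qualification, Day 1). These reviews cover the non-pregnant requirement of criterion 8a but are not hCG tests. The test in Section 9.5.4 is unscheduled. Neither the Amendment 1 summary of changes nor the administrative clarification letters shown alter footnote m.

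**Step 5: bound the number affected.** Section 3.3 plans 3 subjects, with possible expansion to 6. The affected number is anywhere from 0 to 3, or 0 to 6. That is the whole logical range, not an estimate.

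**The case against.** The strongest reply is that no rule is broken. Nothing in the protocol says that every woman of childbearing potential must be tested. Footnote m uses the same two categories as criterion 8a, and Section 6.3.1 sits under a contraception heading. Testing only women who are not sterilized, while asking a tubally sterilized woman for a second method, could be defended as a coherent plan. It is true that no explicit testing rule is violated, and the point does not rest on one. But Section 6.3.1 says its definition is for the purposes of the study, and the protocol gives no reason for testing a narrower group.

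A second reply is that the root conflict lies between 8a and 6.3.1. Under 8a, surgical sterility and contraception are alternatives; under 6.3.1, a woman with a tubal ligation still needs a second method. This observation is fair and it stands. It does not close the testing gap, which can be fixed without settling it.

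Third, the existing controls are substantial. Exclusion 16 bars women unwilling to follow Section 6.3, Section 4.2 requires confirmed eligibility before treatment, and study-center visits are at most 4 weeks apart during treatment. These reduce the risk and are why the point is minor, but none is a scheduled hCG test.

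Finally, leaving footnote m on the FSH row might deny a sterilized woman aged 55 or under the FSH result needed to call her post-menopausal. If so, she stays of childbearing potential under Section 6.3.1 and would be tested by default, so the error is on the safe side.

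**Conclusion.** The concern holds. The testing group in footnote m does not match the study's own definition of childbearing potential, and a pre-menopausal woman with only tubal occlusion or bilateral salpingectomy falls into the gap. She loses 10 or 11 of 11 scheduled tests, including every one from Day 1, over up to 26 weekly doses.

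This rests on reading surgically sterile in footnote m as criterion 8a illustrates it. Whether the screening test survives depends on how Appendix B is read against the footnote, and the documents do not settle that.

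The safety effect is small, and in a study of 3 to 6 subjects it may be nil. The documents give no pregnancy rate for such women, so no probability of harm can be put on it. No efficacy analysis is affected. The case for acting is that the correction is very cheap and makes detection independent of suspicion.

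**What to change.** Give the pregnancy-test row its own footnote, reading: *women of childbearing potential as defined in Section 6.3.1*. Leave footnote m on the FSH row. Criterion 8a and the synopsis need no change to close the testing gap; aligning 8a with Section 6.3.1 on contraception is a separate question.

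The cost is one minor amendment under Section 12.1: investigator agreement, notice to the regulatory authority and the IEC/IRB, and their approval if the change is judged likely to affect safety or conduct. The added assays are at most 11 per affected woman, so 11 × 3 = 33 if all 3 subjects were affected and 11 × 6 = 66 if all 6 were. No visit or venipuncture is added, because the Extended Lipid Panel already needs a blood draw at all 11 visits. Section 6.3.1 already applies to these women, so there is no new contraception requirement.

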# Appendix B List of Laboratory Analytes

#### Appendix B List of Laboratory Analytes

Clinical Chemistry Panel	Screening Tests	Hematology	Extended Urinalysis
Sodium Potassium Chloride Bicarbonate Total protein Albumin Calcium Magnesium Phosphorus	
 
Screening Tests
 
Hepatitis B surface antigen
 
Hepatitis C antibody
 
HIV antibody
 
FSH (women only)
 
Serum βhCG
 
TSH
 
Free T4
 
	
 
Hematology
 
Red blood cells
 
Hemoglobin
 
Hematocrit
 
MCV, MCH, MCHC
 
Platelets
 
White blood cells
 
WBC Differential (% and absolute) 
 
Neutrophils
 
Eosinophils
 
 
 
	Extended Urinalysis 
 
Routine Urinalysis
 
Color
 
Appearance
 
Specific gravity
 
pH
 
Protein
 
Blood
 
Glucose
 
Ketones
 
Bilirubin
 

 
Glucose
 
BUN
 
Creatinine
 
Uric Acid
 
Total bilirubin
 
Direct (conjugated) bilirubin
 
Indirect (unconjugated)
 
	
 
Extended Lipid Panel
 
Total Cholesterol (TC)
 
LDL cholesterol (LDL-C)
 
HDL cholesterol
 
	
 
Basophils
 
Lymphocytes
 
Monocytes
 
 Pharmacokinetics  
 
ISIS 703802 levels in plasma
 
	
 
Urobilinogen
 
Leukocyte esterase
 
Nitrate
 
Microscopic examinatio
 
P/C Ratio (UPCR)
 
A/C Ratio (UACR)
 

 
bilirubin
 
ALT
 
AST
 
Alkaline phosphatase
 
	
 
(HDL-C)
 
Triglycerides (TG)
 
VLDL cholesterol (VLDL-C)
 
	Immunogenicity • Anti-ISIS 703802 antibodies	
 
24-Hour Urine Test
 
Creatinine clearance
 
Protein
 
Albumin
 

Creatinine kinase

GGT

Cys-C

	
 
Non-HDL cholesterol (Non- HDL-C)
 
Lp(a)
 
FFA
 
	Liver Biomarkers (Biomarkers of liver apoptosis and fibrosis) • CK18 • PIIINP	Mixed Meal Test 
 
Plasma glucose
 
FFA
 

PD Panel         • ANGPTL3         • Insulin         • Proinsulin         • C-peptide         • Fructosamine         • Glycated albumin         • Delipidated Free Glycerol         • Fasting Plasma Glucose         Coagulation         • aPTT (sec)	
 
ApoB
 
ApoB-48
 
ApoB-100
 
Apo A-1
 
ApoCIII (total, chylomicron, LDL, HDL, VLDL)
 
Delipidated Free Glycerol
 
Ceramides
 
Sphingolipids
 
Diacyglycerol
 
	
 
Inflammatory
 
hs-CRP
 
IL-6
 
IFN gamma
 
TNF alpha
 
Leptin
 
Adiponectin
 
 Genetic Testing 
 
Genetic sequencing of FPL causing genes
 
	
 
C-peptide
 
Insulin
 
Serum ghrelin
 
GIP
 
GLP-1
 
PYY
 
Incretin hormones
 

-			

1 Plasma PK samples may also be used for profiling of drug binding proteins, bioanalytical method validation purposes, stability assessments, metabolite assessments, or to assess other actions of ISIS 703802 with plasma constituents

2 All samples will be collected, handled and stored under the conditions specified for the assays. Please refer to the study Laboratory Manual for details on the appropriate handling and storage methods for biomarker and other samples.

3 Blood will be collected to assess genetic evidence of FPL (e.g., mutations in LMNA, PPAR-γ, AKT2, CIDEC, PLIN1 genes). May not be collected if adequate genetic data are available in medical history or if patient does not consent to genetic testing

# Appendix C PK Sampling Schedule

# Appendix C PK Sampling Schedule

		Treatment Period						Follow-up Period			
Study Week	1	5	9	13	17	21	25	27	4*	8*	13*
Study Day	D1	D29	D57	D85	D113	D141	D169	D183	* Weeks from the end of treatment period 		
	Pre-dose	Pre-dose	Pre-dose	Pre-dose	Pre-dose	Pre-dose	Pre-dose	Anytime	Anytime	Anytime	Anytime

Note: D, Day

1 Treatment period is defined as the time from the first dose through one dosing interval post last dose

# Appendix D Grading Scale for Adverse Events Relating to Laboratory Abnormalities

# Appendix D Grading Scale for Adverse Events Relating to Laboratory Abnormalities

The following grading recommendations for adverse events relating to lab test abnormalities are based upon the Common Terminology Criteria for Adverse Events (CTCAE) Version 4.03, June 2010.

Adverse Event	Mild	Moderate	Severe		
	Hema	atology			
aPTT prolonged	>ULN - 1.5 x ULN	>1.5 - 2.5 x ULN	>2.5 x ULN; hemorrhage		
Eosinophils increased †	650 – 1,500 cell/mm³	1,501 - 5,000 cell/mm 	>5,000 cell/mm 		
Fibrinogen decreased	<1.0 - 0.75 x LLN or <25% decrease from baseline	<0.75 - 0.5 x LLN or 25 - <50% decrease from baseline	<0.5 x LLN or ≥50% decrease from baseline		
Hemoglobin decreased (Anemia)	Hemoglobin (Hgb) <lln -="" 10.0="" dl;
<lln -="" 100="" 6.2="" <lln="" g="" l;="" l<="" mmol="" td="">Hgb <10.0 - 8.0 g/dL; <6.2 - 4.9 mmol/L; <100 - 80g/L	Hgb <8.0 g/dL; <4.9 mmol/L; <80 g/L; transfusion indicated	</lln></lln>	Hgb <10.0 - 8.0 g/dL; <6.2 - 4.9 mmol/L; <100 - 80g/L	Hgb <8.0 g/dL; <4.9 mmol/L; <80 g/L; transfusion indicated		
Hemoglobin increased	Increase in >0 - 2 g/dL above ULN or above baseline if baseline is above ULN	Increase in >2 - 4 g/dL above ULN or above baseline if baseline is above ULN	Increase in >4 g/dL above ULN or above baseline if baseline is above ULN		
INR increased	>1 - 1.5 x ULN; >1 - 1.5 times above baseline if on anticoagulation	>1.5 - 2.5 x ULN; >1.5 - 2.5 times above baseline if on anticoagulation	>2.5 x ULN; >2.5 times above baseline if on anticoagulation		
Lymphocyte count decreased	<lln -="" 800="" mm3; <lln -="" 0.8="" 109/L</lln></lln>	<800 - 500/mm³; <0.8 - 0.5 x 10  /L	<500 /mm  ; <0.5 x 10  /L		
Lymphocyte count increased	-	>4000/mm  - 20,000/mm 	>20,000/mm 		
Neutrophil count decreased	<lln -="" 1500="" mm³;
<lln -="" 1.5="" 109 /L</lln></lln>	<1500 - 1000/mm³; <1.5 - 1.0 x 10  /L	<1000/mm³; <1.0 x 10  /L		
Platelet count decreased	<lln -="" 75,000="" mm3; <lln -="" 109 /L</lln></lln>	<75,000 - 50,000/mm  ; <75.0 - 50.0 x 10  /L	<50,000/mm  ; <50.0 x 10  /L		
White blood cell decreased	<lln -="" 3000="" mm3; <lln -="" 109 /L</lln></lln>	<3000 - 2000/mm  ; <3.0 - 2.0 x 10  /L	<2000/mm  ; <2.0 × 10  /L		
	Che	mistry			
Acidosis	pH <normal, but="">=7.3</normal,>	-	pH <7.3		
Alanine aminotransferase increased	>ULN - 3.0 x ULN	>3.0 - 5.0 x ULN	>5.0 x ULN		
Alkaline phosphatase increased	>ULN - 2.5 x ULN	>2.5 - 5.0 x ULN	>5.0 x ULN		
Alkalosis	pH >normal, but ≤7.5	-	pH >7.5		
Aspartate aminotransferase increased	>ULN - 3.0 x ULN	>3.0 - 5.0 x ULN	>5.0 x ULN		
Blood bilirubin increased	>ULN - 1.5 x ULN	>1.5 - 3.0 x ULN	>3.0 x ULN		
Cardiac troponin I increased	Levels above the upper limit of normal and below the level of myocardial infarction as defined by the manufacturer	-	Levels consistent with myocardial infarction as defined by the manufacturer		

# Appendix DGrading Scale for Adverse Events Relating to Laboratory Abnormalities Continued

Adverse Event	Mild	Moderate	Severe
Cardiac troponin T increased	Levels above the upper limit of normal and below the level of myocardial infarction as defined by the manufacturer	-	Levels consistent with myocardial infarction as defined by the manufacturer
CD4 lymphocytes decreased	<lln -="" 500="" mm3; <lln -="" 0.5="" 109 /L</lln></lln>	<500 - 200/mm  ; <0.5 - 0.2 x 10  /L	<200/mm  ; <0.2 x 10  /L
CPK increased*	>ULN - <6 ULN	6 - 10 x ULN	>10 x ULN
Creatinine increased	>1 - 1.5 x baseline; >ULN - 1.5 x ULN	>1.5 - 3.0 x baseline; >1.5 - 3.0 x ULN	>3.0 x baseline; >3.0 x ULN
GGT increased	>ULN - 2.5 x ULN	>2.5 - 5.0 x ULN	>5.0 x ULN
Hypercalcemia	Corrected serum calcium of >ULN - 11.5 mg/dL; >ULN - 2.9 mmol/L; Ionized calcium >ULN - 1.5 mmol/L	Corrected serum calcium of >11.5 - 12.5 mg/dL; >2.9 - 3.1 mmol/L; lonized calcium >1.5 - 1.6 mmol/L; symptomatic	Corrected serum calcium of >12.5 mg/dL; >3.1 mmol/L; lonized calcium >1.6 mmol/L; hospitalization indicated
Hyperglycemia	Fasting glucose value >ULN - 160 mg/dL; Fasting glucose value >ULN - 8.9 mmol/L	Fasting glucose value >160 - 250 mg/dL; Fasting glucose value >8.9 - 13.9 mmol/L	>250 mg/dL; >13.9 mmol/L; hospitalization indicated
Hyperkalemia	>ULN - 5.5 mmol/L	>5.5 - 6.0 mmol/L	>6.0; hospitalization indicated
Hypermagnesemia	>ULN - 3.0 mg/dL; >ULN - 1.23 mmol/L	-	>3.0 mg/dL; >1.23 mmol/L
Hypernatremia	>ULN - 150 mmol/L	>150 - 155 mmol/L	>155 mmol/L; hospitalization indicated
Hyperuricemia	>ULN - 10 mg/dL (0.59 mmol/L) without physiologic consequences	-	>ULN - 10 mg/dL (0.59 mmol/L) with physiologic consequences
Hypoalbuminemia	<lln -="" 3="" dl;
<lln -="" 30="" g="" l<="" td=""><3 - 2 g/dL; <30 - 20 g/L	<2 g/dL; <20 g/L	</lln></lln>	<3 - 2 g/dL; <30 - 20 g/L	<2 g/dL; <20 g/L
Hypocalcemia	Corrected serum calcium of <lln -="" 8.0
mg/dL; <lln -="" 2.0="" l;="" lonized
calcium <lln -="" 1.0="" l<="" mmol="" td="">Corrected serum calcium of <8.0 - 7.0 mg/dL; <2.0 - 1.75 mmol/L; lonized calcium <1.0 - 0.9 mmol/L; symptomatic	Corrected serum calcium of <7.0 mg/dL; <1.75 mmol/L; lonized calcium <0.9 mmol/L; hospitalization indicated	</lln></lln></lln>	Corrected serum calcium of <8.0 - 7.0 mg/dL; <2.0 - 1.75 mmol/L; lonized calcium <1.0 - 0.9 mmol/L; symptomatic	Corrected serum calcium of <7.0 mg/dL; <1.75 mmol/L; lonized calcium <0.9 mmol/L; hospitalization indicated
Hypoglycemia	<lln -="" 55="" dl;
<lln -="" 3.0="" l<="" mmol="" td=""><55 mg/dL; <3.0 mmol/L	<40 mg/dL (<2.2 mmol/L) AND requires assistance of another person to actively administer carbohydrates, glucagon, or take other corrective actions‡	</lln></lln>	<55 mg/dL; <3.0 mmol/L	<40 mg/dL (<2.2 mmol/L) AND requires assistance of another person to actively administer carbohydrates, glucagon, or take other corrective actions ‡
Hypokalemia	<lln -="" 3.0="" l<="" mmol="" td=""><lln -="" 3.0="" l;="" mmol="" symptomatic;
intervention indicated</lln>	<3.0 mmol/L; hospitalization indicated	</lln>	<lln -="" 3.0="" l;="" mmol="" symptomatic;
intervention indicated</lln>	<3.0 mmol/L; hospitalization indicated
Hypomagnesemia	<lln -="" 1.2="" dl;
<lln -="" 0.5="" l<="" mmol="" td=""><1.2 - 0.9 mg/dL; <0.5 - 0.4 mmol/L	<0.9 mg/dL; <0.4 mmol/L	</lln></lln>	<1.2 - 0.9 mg/dL; <0.5 - 0.4 mmol/L	<0.9 mg/dL; <0.4 mmol/L
Hyponatremia	<lln -="" 130="" l<="" mmol="" td="">-	<130 mmol/L	</lln>	-	<130 mmol/L
Hypophosphatemia	<lln -="" 2.5="" dl;
<lln -="" 0.8="" l<="" mmol="" td=""><2.5 - 2.0 mg/dL; <0.8 - 0.6 mmol/L	<2.0 mg/dL; <0.6 mmol/L	</lln></lln>	<2.5 - 2.0 mg/dL; <0.8 - 0.6 mmol/L	<2.0 mg/dL; <0.6 mmol/L
Lipase increased	>ULN - 1.5 x ULN	>1.5 - 2.0 x ULN	>2.0 x ULN
Serum amylase increased	>ULN - 1.5 x ULN	>1.5 - 2.0 x ULN	>2.0 x ULN

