#### Severe Hypoglycemia

Requires assistance of another person to actively administer carbohydrates, glucagon, or take other corrective actions. Glucose concentrations may not be available during an event. Neurological recovery following glucose levels returning to normal considered sufficient evidence that event was induced by low glucose concentration.

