#### Probable Symptomatic Hypoglycemia

Typical hypoglycemia symptoms not accompanied by blood glucose determination but likely caused by blood glucose  $\leq$  70 mg/dL ( $\leq$  3.9 mmol/L).

A **documented severe hypoglycemic event** is defined as one in which the subject requires assistance of another person to obtain treatment for the event and has a blood glucose level  $\leq$  70 mg/dL ( $\leq$  3.9 mmol/L). The rescue treatment of hypoglycemia may include IV glucose or buccal or intramuscular glucagon.

The definition of severe symptomatic hypoglycemia includes all episodes in which neurological impairment was severe enough to prevent self-treatment and which were thus thought to place subjects at risk for injury to themselves or others.

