#### 9.4.3.2 Severity

The severity of AEs and SAEs will be graded based on criteria from the Common Terminology Criteria for Adverse Events (CTCAE) Version 4.03, June 2010 (refer to Appendix D). Any AE not listed in Appendix D will be graded as follows:

- Mild: The event is easily tolerated by the subject and does not affect the subject's usual daily activities
- **Moderate:** The event causes the subject more discomfort and interrupts the subject's usual daily activities
- Severe: The event is incapacitating and causes considerable interference with the subject's usual daily activities

If the event is an SAE, then all applicable seriousness criteria must be indicated (criteria listed in Section 9.3.3).

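### Hypoglycaemia needing another person's help is severe under Section 8.5.6, but at 40 mg/dL or above Appendix D, which Section 9.4.3.2 applies, grades it moderate or mild

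*Combined protocol and SAP*

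**What the plan says.** Three places in Amendment 1 bear on how a hypoglycaemic event is graded.

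- **Section 8.5.6, Safety Monitoring for Hypoglycemia.** Severe hypoglycaemia is defined by need for another person's help. No glucose value is required: "Glucose concentrations may not be available during an event", and "Neurological recovery following glucose levels returning to normal considered sufficient evidence" that low glucose caused the event. A documented severe event "is defined as one in which the subject requires assistance of another person to obtain treatment for the event" and in which glucose is at or below 70 mg/dL. The section adds: "The definition of severe symptomatic hypoglycemia includes all episodes" in which neurological impairment prevented self-treatment.
- **Section 9.4.3.2, Severity.** "The severity of AEs and SAEs will be graded based on criteria from the Common Terminology Criteria", version 4.03, with a reference to Appendix D. A functional scale is kept in reserve: "Any AE not listed in Appendix D will be graded as follows". On that scale severe means "The event is incapacitating and causes considerable interference" with usual daily activities.
- **Appendix D, Hypoglycemia row.** Mild runs from below the LLN down to 55 mg/dL, moderate is below 55 mg/dL, and severe is below 40 mg/dL "AND requires assistance of another person to actively administer carbohydrates", glucagon or other corrective action. A footnote says this grading was modified to agree with diabetes-society guidelines.

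The severe cell reads the same in the November 2017 protocol and in Amendment 1, so the conjunction is not a text-extraction error.

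**The concern.** Hypoglycaemia is listed in Appendix D, so on a plain reading of Section 9.4.3.2 the Appendix D row sets the grade. That row adds a numeric condition that Section 8.5.6 does not have. The same clinical event, a subject who could not treat himself or herself and needed help, is severe in one section and can be moderate or mild in the other. No sentence says which prevails.

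Hypoglycaemia is a foreseeable event in this trial. Every subject has diabetes on glucose-lowering therapy, which may include insulin (inclusion criterion 4), and the dose is expected to improve glycaemic control (Section 2.5). Safety and tolerability is a secondary objective. With 3 subjects planned and at most 6, individual event records carry much of the safety evidence, so one misgraded event would be noticeable.

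The monitoring instructions also make the 40 mg/dL condition hard to document. Under Section 8.5.6, subjects in doubt about their safety treat first and measure glucose afterwards. In an assisted event the only reading may be missing or may already be raised by treatment.

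**Working it through.** The plan states no figure on this point. The check is to apply the two rules to the same assisted events.

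**Inputs**

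- Section 8.5.6: severe if assistance is needed; documented severe if assistance is needed and glucose is at or below 70 mg/dL.
- Appendix D: severe if glucose is below 40 mg/dL and assistance is needed; otherwise moderate if below 55 mg/dL; otherwise mild if below the LLN.
- LLN for glucose: not given in the documents. Assumed to be 60, 65 or 70 mg/dL.

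**Assisted events under each rule**

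| Glucose (mg/dL) | Section 8.5.6 | Appendix D |
|---|---|---|
| below 40 | severe | severe |
| 40 to below 55 | severe | moderate |
| 55 to below LLN | severe | mild |

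**Examples** (mmol/L = mg/dL ÷ 18.016)

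- 45 mg/dL, assisted: 45 ÷ 18.016 = 2.50 mmol/L. Severe under Section 8.5.6. It is not below 40 but is below 55, so it is moderate under Appendix D.
- 58 mg/dL, assisted: 58 ÷ 18.016 = 3.22 mmol/L. Severe under Section 8.5.6. It is not below 55, so it is mild under Appendix D if the LLN is above 58, as it is for all three assumed values.

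**Dependence on the LLN.** The moderate band, 40 to below 55 mg/dL, is the same whatever the LLN. The mild band ends at 60, 65 or 70 mg/dL under the three assumptions.

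**Unit check.** 40 ÷ 18.016 = 2.22 and 55 ÷ 18.016 = 3.05 mmol/L, which agrees with the printed 2.2 and 3.0 to within 0.05 mmol/L. The conflict does not come from a conversion error.

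**Where the grade is used**

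- SAE status: Section 8.5.6 makes severe hypoglycaemia an SAE only if it meets the SAE criteria. Unaffected.
- Stopping rules: Sections 8.6.1 to 8.6.3 cover liver, renal and platelet results. Unaffected.
- Planned adverse event tables: Section 10.6.2.1 tabulates by system organ class and preferred term, and summarises by treatment emergence, relatedness and seriousness. Severity is not used.
- Summary by severity: Section 10.6.2 plans one only for injection site reactions.
- Listings (Section 10.6) and narratives (Section 10.6.2.1): these can show the recorded grade, so they are affected.

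**The case against.** The strongest defence is that the two sections do different jobs. The Section 8.5.6 categories stand under a heading about classifying hypoglycaemia and serve monitoring and management; they are not expressly intensity grades. Appendix D describes its contents as recommendations for adverse events relating to laboratory abnormalities. Section 9.5.1 prefers the underlying diagnosis to the laboratory value as the adverse event term. An investigator could therefore record an assisted episode as a clinical event, use the functional scale in Section 9.4.3.2, and grade it severe as incapacitating.

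That reading is possible, but it does not remove the conflict. Section 9.4.3.2 reserves the functional scale for events not listed in Appendix D, and hypoglycaemia is listed. The severe cell also uses the same assistance criterion as Section 8.5.6, so it is addressing the same clinical event. Two investigators could grade one event differently, each with support in the text.

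Other parts of the defence do stand, and they limit the point:

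- A reader might infer that an assisted event with no reading cannot be graded. With no glucose value there is no laboratory abnormality to place in the table, and the functional scale is a natural fallback.
- A reader might infer that the cut-off would lower a reported count of severe hypoglycaemia or hide events. No planned table counts hypoglycaemia by severity. The event, its glucose values and the treatment given are all to be recorded, and all case report form data are listed.
- A reader might infer that most assisted events would be under-graded. The documents say nothing about how such events are distributed over glucose values.
- A reader might conclude that the 40 mg/dL threshold is itself an error to be deleted. The footnote shows it was set deliberately with reference to external guidelines. Whether it matches them cannot be checked here, so the documents do not support removing it.

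**Conclusion.** The inconsistency is real and minor. Followed as written, Section 9.4.3.2 with Appendix D records an assisted event at 40 to below 55 mg/dL as moderate, and one from 55 mg/dL to below the LLN as mild, while Section 8.5.6 calls both severe. The first band needs no assumption. The second exists only if the LLN is above 55 mg/dL. Both rest on the plain reading that Appendix D governs every event it lists.

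The consequence is a recorded grade that is too low for an individual event, on the adverse event form and in listings and narratives. How often this will happen cannot be derived from the documents.

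**What to change.** Add one sentence to Section 9.4.3.2: hypoglycaemia that meets the Section 8.5.6 definition of severe (assistance of another person required, with or without a glucose reading) is graded severe regardless of the glucose cut-off in Appendix D.

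This leaves the Appendix D cell as it stands and settles the grade of events with no reading. Unassisted readings below 40 mg/dL stay moderate, as now. No visit, procedure, eligibility criterion or analysis changes. The cost is one sentence, and the only downside is that an individual event may carry a less favourable grade.
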